5.3 Questionnaires

Demographic information: Name, marital status, date of birth; racial/ethnic group; occupation; education.

Personal medical history: Select questions about the participant's medical history, past and present.

Dietary intake: Participants will be asked to complete Mediterranean Diet 14 item dietary screener.

Current medications: Prescription medications; participants will be instructed to bring medications to the clinic.

Intervention Assessments (see appendix A)

Compliance-Intake of the study foods, tree nuts and EVOO will be tracked on a daily basis using a compliance diary. The participant will record on a daily diary the following information:
Did you eat the nuts today? - Yes, No
Did you consume the oil today? -Yes, No

Telephone contacts and maintenance of the cohort: Telephone contact will be used to monitor participants for study compliance and side effects by phone at the end of week 1 and 2. During the phone call participants will be invited to ask any questions and to discuss any problems with the study, specifically their adherence to the study foods. Participants' medication history will be reviewed.

Perception of Epigenetic Age Assessment -For participants of the intervention arm 1 (participants educated about epigenetic age acceleration), a self-administered exit questionnaire will be given to qualitatively explore participants' perception of epigenetic age, and challenges and motivators for behavior change during the intervention. The questions will be designed to ascertain understanding of epigenetic age, and assess the challenges and motivators participants encountered during the intervention.

Intervention Experience Assessment- Participants in both study arms will be administered an intervention experience assessment to explore how participants' experiences would impact the feasibility of a larger clinical intervention in terms of challenges and motivators.

5.4 Duration of Participation in Intervention

Participation will be for a 4-week period unless the following occur:

- Illness that prevents further administration of treatment
- Unacceptable adverse event(s)
- Patient decides to withdraw from the study
- General or specific changes in the participant's condition render the patient unacceptable for further treatment in the judgment of the investigator

5.5 Duration of Follow Up

Participants will be involved in the study intervention for a period of 4 weeks. Participants removed from study for unacceptable adverse events will be followed until resolution or stabilization of the adverse event.

5.6 Criteria for Removal from Study

Participants will be removed from study when any of the criteria listed above applies. The reason for study removal and the date the participant was removed will be documented in the Case Report Form.

The study is set to end on March 31, 2022. As such, all study intervention visits need to be completed by March 3, 2022. Any participants remaining on study, that have not attended their intervention visit by that date, will be discontinued from the study.

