4.1 Toxities

Side effects will be monitored by staff contact at the end of week 1 visit, and at the end of week 2 (by phone) and at the final measurement visit at the end of week 4. Participants will be encouraged to contact the Study manager during the study period if they feel they are experiencing effects related to the study foods.

EVOO and tree nuts are generally recognized as safe and are consumed by free living adults on a regular basis. The amount to be given in this study are within the range given to the participants in the PREDIMED study [6] and found to have only minor side effects, mainly stomach upset, bloating and nausea, and none of the side effects advanced to serious adverse events.

Administration

Study foods will consist of one ounce of tree nuts per day and two tablespoons of EVOO per day. Participants will be instructed how to consume the proper amount of tree nuts and EVOO and reporting the consumption on the compliance diary (Appendix A). The tree nuts will be provided in daily servings (one ounce per day) and EVOO will be provided in bottles, along with a tablespoon. Participants will be instructed to use the tablespoon to measure EVOO. Participants will also receive recipes and other written information that will assist them in incorporating both the nuts and EVOO into their existing dietary patterns.

Dose Modification/Toxicity management:

Side effects will be monitored via the telephone visit at the end of week 1 and 2 and by participant report. Participants will be encouraged to contact the study team during the study period if they feel they are experiencing side effects related to the study foods. For those participants with existing medical conditions (e.g., gallbladder removal or bariatric surgery) or who are experiencing nausea related to consumption of the olive oil, a titrated dosing plan will be used. These participants will begin their olive oil consumption at 1 tablespoon/day for 5 days and increasing to 2 tablespoons/day on the sixth day if it is well tolerated. If this increase is not tolerated, the participant can be returned to 1 tablespoon per day and attempt an increase after an additional 5 days.

Withdrawal from study intervention

Any side effects experienced by the participant may or may not be due to the study foods. If the side effects become intolerant for the participant, he/she may be withdrawn from the study at the discretion of the study team.

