4.2 Table of Study-Related Interventions

Measure	Baseline: In-person screening visit	Intervention visit	End of Week 1 Phone Call	End of week 2 Phone Call	Final in person visit
Anthropometrics					
Body weight	X				X
Height	X				X
Waist circumference	X				X
Blood collection	X	X			X
Blood pressure	X				X
Demographics	X				
Mediterranean diet screener	X				X
Health History/health habits	X				X
Adherence/safety assessment			X	X	X
Intervention Experience Assessment and Perception of Epigenetic Age Assessment (arm 1 only)					X
Dispense study foods		X			

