4.3.3 End of week 1 and week 2 telephone calls

During the end of week 1 telephone call, participants will be contacted via telephone and asked questions about their adherence, and any potential side effects observed. Participants will receive additional counseling for how to incorporate the nuts and oil into a daily meal as needed. A follow up phone call at the end of week 2 will be scheduled to assess compliance and to answer participant questions, and a final measurement visit will be scheduled for the end of week 4 for a morning time and participants will be asked to be fasting.

4.3.4 Final measurement visit, end of week 4

The same measures, as listed in the in-person screening visit will be performed. Study questionnaires, with the exception of demographics and health history, will be distributed and completed, and adherence diaries will be collected.

For participants of the intervention arm 1 (participants educated about epigenetic age acceleration), a self-administered exit questionnaire will be given to qualitatively explore participants' perception of epigenetic age, and challenges and motivators for behavior change during the intervention. The open-ended questions will be designed to ascertain understanding of epigenetic age, and assess the challenges and motivators participants encountered during the intervention.

Participants in both arms will be administered an Intervention Experience Assessment to explore how participants' experiences would impact the feasibility of a larger clinical intervention in terms of challenges and motivators.

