8.3 Participants' perception of epigenetic age, challenges and motivators

Primary outcome 5: Perception of Epigenetic Aging Assessment and Intervention Experience Assessment

To gain preliminary data supporting the feasibility of testing epigenetic age acceleration as a motivating factor for behavior change in a larger trial, participants of the intervention arm 1 (participants educated about epigenetic age acceleration), will be given a self-administered exit questionnaire to qualitatively explore participants' perception of epigenetic age. All participants will be given a self-administered Intervention Experience Assessment to explore participant experiences in the study, and the challenges and motivators for behavior change during the intervention. The \ questions will be designed to ascertain understanding of epigenetic age, and assess the challenges and motivators participants encountered during the intervention. All participants will be asked if they can be contacted for future studies.

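### Appendix C, part of Primary Outcome 5, is scheduled only at week 4, so people removed for intolerance or illness are never asked to complete it

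*Combined protocol and SAP*

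**What the plan says.** Section 8.3 makes two questionnaires Primary Outcome 5. The Perception of Epigenetic Age form (Appendix D) goes to arm 1. For the other, Appendix C, 8.3 states: "All participants will be given a self-administered Intervention Experience Assessment to explore participant experiences in the study". Section 4.3.4 agrees ("Participants in both arms will be administered an Intervention Experience Assessment"), as does 5.3 ("Participants in both study arms will be administered an intervention experience assessment"). Section 4.3.4 is the text for the final visit, and the schedule table in 4.2 has a single mark for the two forms. No other time is given for either.

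Section 5.4 lists what can end the 4-week intervention early: "Illness that prevents further administration of treatment", an unacceptable adverse event, the participant's own decision, or a change in condition. Section 5.6 then says "Participants will be removed from study when any of the criteria listed above applies", with the reason and date entered in the case report form. For side effects that become intolerable, 4.1 says "he/she may be withdrawn from the study at the discretion of the study team". The only later contact described is in 5.5: "Participants removed from study for unacceptable adverse events will be followed until resolution or stabilization of the adverse event".

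**The concern.** The purpose of Primary Outcome 5 is to learn the challenges and motivators that bear on a larger trial. Someone who had to stop the foods is well placed to describe the challenges. Yet 5.6 and 4.1 treat stopping the foods as leaving the study, and the form is tied to a visit that person no longer attends.

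At stake is whether Appendix C describes everyone who started the foods or only those who reached week 4. If those removed found the foods harder than the rest did, which is likely but not something the documents establish, a completer-only summary would understate difficulty and overstate willingness to continue for 3-4 years.

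**Working it through.** **1. Where the forms are scheduled.** Final in-person visit: yes (4.2, 4.3.4). Week 1 and week 2 calls: adherence and safety only (4.2, 4.3.3). At removal: reason and date (5.6). After removal for an adverse event: follow-up of the event (5.5). No early-termination visit, call or mailing is named for Appendix C or D. Nothing forbids one either.

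**2. Who is affected.** Only people removed after foods were dispensed.
- Those discontinued under 5.6 for missing the March 3, 2022 date for the intervention visit never received foods.
- Those titrated for oil nausea (4.1) stay in the study.
- Those who stop a food without being removed count as non-adherent under 8.2 and can still complete the form at week 4.
- Those who withdraw by their own decision may decline any form.

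That leaves mainly removals for illness, intolerance or other adverse events within 4 weeks.

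**3. What is still known about a removed person.**

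| Information | Captured without Appendix C? |
|---|---|
| That they stopped, when and why | Yes: 5.6, and adverse event reports under section 6.0 |
| Barriers in their own words (item 17) | In part: diary comment space (Appendix A), with diaries collected at week 1 (4.0); problems raised on the calls (5.3) |
| Difficulty ratings (items 3-4) | No |
| Suggestions for future studies (item 18) | No |
| Could they take part for 3-4 years (item 16) | Not asked, though often predictable from the removal reason |

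Later diaries are collected at week 4 (4.3.4), so the diary route is incomplete for someone removed after week 1.

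**4. Scale.** Section 8.3 plans no numeric estimate for Primary Outcome 5, and the documents give no removal rate, so the counts below are assumptions. Take n = 50 dispensed foods, k removed without a form, and 60% answering yes to an item such as item 16.

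- Share left undetermined = k/n.
- Full width of the 95% interval among responders = 2 × 1.96 × √(0.6 × 0.4/(n − k)).

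| k | Undetermined (points) | Interval width (points) | Ratio |
|---|---|---|---|
| 1 | 1/50 = 2.0 | 3.92 × √(0.24/49) = 27.4 | 7% |
| 2 | 2/50 = 4.0 | 3.92 × √(0.24/48) = 27.7 | 14% |
| 5 | 5/50 = 10.0 | 3.92 × √(0.24/45) = 28.6 | 35% |

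The same thing can be shown as bounds. If 80% of 45 responders say yes (36 people, assumed), the proportion among all 50 lies between 36/50 = 72% and 41/50 = 82%. With 10 removed it lies between 32/50 = 64% and 42/50 = 84%; with 15 removed, between 28/50 = 56% and 43/50 = 86%. The last two cases are an outer range. Nothing in the documents suggests losses that large from intolerance.

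**5. The plan's own figure.** The only design calculation is in 8.6: power 0.80 with 50 people and a 0.4 SD difference. It reproduces, since Φ(0.4 × √50 − 1.96) = Φ(0.868) = 0.807. It concerns epigenetic age and has no bearing on this point.

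**The case against.** The strongest reply is that the plan is consistent as it stands. In 8.3 the phrase about all participants directly follows a sentence limiting the other form to arm 1, so its natural meaning is both arms, as 4.3.4 and 5.3 say. A reader might infer that 8.3 makes a promise the schedule breaks. The documents do not require that reading, and the point does not depend on it.

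A reader might also infer that everything these people could say about barriers is lost. That is too strong: diary comments, the two calls, adverse event reports and the removal reason all carry some of it.

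The group is also narrow. Known allergy is screened out (2.1.5), oil nausea is titrated, withdrawal under 4.1 is discretionary, 4.1 describes only minor side effects at comparable amounts, and exposure lasts 4 weeks. Appendix D is mainly about perceptions of epigenetic age, so the argument that people who stop are especially informative barely applies to it.

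All of this stands, and it limits the size of the point. It does not supply the missing ratings, suggestions and answers on a longer study, and it does not give staff a stated time to ask for them.

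**Conclusion.** The plan, followed as written, collects Appendix C only from those who reach week 4, and so omits people removed for intolerance or illness from a primary outcome about barriers to a longer trial. This is a gap worth closing cheaply, not an internal contradiction.

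Its numerical effect is probably minor: 2 to 4 points of a yes/no item if 1 or 2 of 50 are removed, and 10 points if 5 are. Those counts and the 60% are assumptions. The main loss is the content of a few informative answers in a largely qualitative outcome. A reader might go further and conclude that Primary Outcome 5 will be seriously biased. With no removal rate given and several safeguards against removal, the documents do not support that.

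**What to change.** Add one sentence to 5.6, cross-referenced in 4.1 and 4.2: anyone removed after study foods were dispensed is offered Appendix C (and Appendix D in arm 1) and asked to return the diary at the time of removal, in person, by phone or by mail, unless they decline.

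In 8.3, state that Primary Outcome 5 will be reported with the number of forms returned out of those dispensed foods, by arm, and with those who stopped early shown separately.

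The removal rules, titration, adverse event follow-up and the paired tests in 8.4 and 8.5 stay as they are. It is not necessary to redefine stopping the foods as continued participation; that would raise the separate question of whether off-food week-4 samples enter those tests.

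The cost is a short amendment and a few extra contacts, using self-administered forms that already exist. The benefit is limited by timing: the document is dated January 14, 2022 and intervention visits close on March 3, 2022, so the change would reach only removals after it takes effect. The reporting change in 8.3 can be made regardless.

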6.0 Adverse Events and Reporting Requirements

The risk of harm or discomfort that may happen as a result of taking part in this research study is not expected to be more than in daily life or from routine physical or psychological examinations or tests.

There is risk, although minor, involved in obtaining blood samples. There may be some discomfort, bruising and/or bleeding where the needle is inserted for blood draws. Some people become dizzy, lightheaded, or feel faint. Infection may occur on rare occasions. Frequent donation of blood can result in low iron in the blood.

There is also a risk of weight gain from the increased caloric intake that may occur as a result of consuming the nuts and oils. Participants will be provided with recipes and other information on incorporating the nuts and oils by replacing other foods to reduce the risk of weight gain and will be encouraged to contact the study team if they believe they are gaining weight.

There is a slight risk that study participants may have an unknown allergy to nuts or olive oil and may therefore have an allergic reaction to one of these substances. Mild allergic symptoms that can occur include: raised red bumps of skin – hives, swelling of the lips, tingling of the throat and mouth, itchy skin and rash, runny nose, tightening of the throat, and digestive symptoms – cramps, stomach pain, nausea, or vomiting. If study participants feel they are experiencing one of these mild allergic reactions, they will be instructed to contact the study team and report the reaction.

Although unexpected in adults without prior knowledge of an allergy to tree nuts, consumption of tree nuts can also result in severe allergic reaction symptoms including: difficult or noisy breathing, swelling of the tongue, swelling or tightness of the throat, difficulty talking or a hoarse voice, wheeze or persistent cough, or persistent dizziness or collapse. If study participants feel they are experiencing one of these severe allergic reaction symptoms, they will be instructed to call 911 and seek immediate medical care. After treatment, they will be instructed to contact the study team and report the reaction.

Study staff will report any adverse events to the PI, [name], who will review all unanticipated problems involving risk to participants or others, serious adverse events, and provide a written report of the event to the IRB. If necessary, the study team will direct appropriate referrals for health care needed to address study-related adverse events.

Results of routine clinical labs and physical measures obtained as part of study visits that meet the criteria for “Alert Values” will be communicated as described in the table below. The PI, [name], will review medical eligibility criteria as needed, as well as clinical measures and laboratory reports. [name], the Study Medical Director, will serve as the primary contact for staff and participants regarding medical issues and labs and physical measures meeting alert values. [name] will review summaries of alerts on a periodic basis along with the AEs.

Alert Values

Measure	Alert Value	Notify Participant	Notify PCP/Medical Director
Blood Pressure (Avg.)	Level 1 SBP ≥ 180 mm/Hg OR DBP ≥ 110 mm/Hg	In clinic. Advise to follow-up with PCP within 1 week.	Within 1 week. IF symptomatic (e.g. chest pain, headache, short of breath), notify safety officer and/or PCP immediately.
	Level 2 SBP ≥ 160 mm/Hg OR DBP ≥ 100 mm/Hg (and not Level 1 BP)	In clinic. Advise to follow-up with PCP within 1 month.	Within 1 week. IF symptomatic (e.g. chest pain, headache, short of breath), notify safety officer and/or PCP immediately.
	Level 3 SBP ≥ 140 mm/Hg OR DBP ≥ 90 mm/Hg (and not Levels 1 or 2)	In clinic. Advise to follow-up with PCP within 2 months.	Per routine reporting. IF symptomatic (e.g. chest pain, headache, short of breath), notify safety officer and/or PCP immediately.
	SBP ≤ 90 mm/Hg OR DBP ≤ 50 mm/Hg	In clinic. Advise to follow-up with PCP within 1 week.	Within 1 week. IF symptomatic (lightheaded, feels faint), notify safety officer and/or PCP immediately.
Blood glucose	< 50 mg/dl OR > 400 mg/dl	Within 1 week or sooner as indicated by exact value and clinician judgment.	Within 1 week or sooner as indicated by exact value and clinician judgment.
Triglycerides	TG ≥ 1000 mg/dl	Within 1 week or sooner as indicated by exact value and clinician judgment.	Within 1 week or sooner as indicated by exact value and clinician judgment.

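### Section 6.0 puts throat tightness in both the mild allergic list (contact the study team) and the severe list (call 911), and does not say which instruction prevails

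*Combined protocol and SAP*

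**What the plan says.** Two consecutive paragraphs of section 6.0 deal with allergic reactions to the study foods.

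- **Mild tier** (nuts or olive oil). The list includes "itchy skin and rash, runny nose, tightening of the throat, and digestive symptoms". For a participant who feels "one of these mild allergic reactions, they will be instructed to contact the study team and report the reaction", nothing further is stated.
- **Severe tier** (introduced by reference to tree nuts). The list includes "difficult or noisy breathing, swelling of the tongue, swelling or tightness of the throat". The instruction for a participant who feels "one of these severe allergic reaction symptoms, they will be instructed to call 911 and seek immediate medical care" is followed by "After treatment, they will be instructed to contact the study team and report the reaction".

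Other text bears on how a reaction would be handled:

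- Section 4.1 says participants will be "encouraged to contact the Study manager during the study period if they feel they are experiencing effects related to the study foods". On scheduled monitoring it says "Side effects will be monitored by staff contact at the end of week 1 visit, and at the end of week 2 (by phone", and it adds the final visit at the end of week 4.
- Later in section 6.0, the Study Medical Director is named as the main contact for medical issues, and the study team is to arrange referrals where needed.
- Section 2.1.5 keeps out people with a known allergy or hypersensitivity to olive oil or nuts.

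**The concern.** The same symptom carries two different instructions. The severe paragraph makes throat tightness an emergency. The paragraph before it files the same sensation under mild and asks only for a report to the study team.

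The participant has to choose, usually at home. The full four-week supply is handed out at one visit, and staff contacts are few. Known allergy is an exclusion, so anyone who reacts is likely to be having a first reaction and may lean heavily on what they were told. At stake is a delay in emergency care if a participant follows the mild instruction alone. Estimation, testing and sample size are untouched.

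**Working it through.** The plan gives no figure to reproduce here. The check is a comparison of text with a few counts.

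**1. The two lists (section 6.0).**

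| Tier | Entries, paraphrased | Count |
|---|---|---|
| Mild | hives; lip swelling; tingling mouth and throat; itch and rash; runny nose; **throat tightening**; digestive symptoms | 7 |
| Severe | breathing difficulty; tongue swelling; **throat swelling or tightness**; trouble talking or hoarseness; wheeze or lasting cough; lasting dizziness or collapse | 6 |

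Total 7 + 6 = 13 entries. One pair overlaps (2 entries), so 13 − 2 = 11 do not conflict. The counts depend slightly on how compound entries are split. The single overlap does not.

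**2. The trigger.** Both instructions apply to a participant who feels any one symptom on the list. No combination or minimum number is required, so throat tightness alone activates both.

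**3. Does anything separate the entries?** One entry speaks of tightening and the other of tightness. Neither carries a grade, a duration or an accompanying sign. The paragraphs name different foods, but section 4.0 asks every participant to take both foods daily, so the difference does not sort participants or reactions. Nor does the mild paragraph tell a participant to call 911 if symptoms worsen.

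**4. Is it resolved elsewhere?** No.
- Section 4.1 invites contact about effects of the study foods and covers dose titration and withdrawal.
- The rest of section 6.0 names a medical contact and promises referrals. Its alert table covers only blood pressure, glucose and triglycerides.
- Section 6.1 concerns reporting to the IRB.

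None of these ranks the two tiers.

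**5. Scale.** After the foods are dispensed, sections 4.1 and 4.2 schedule three safety contacts: end of week 1, end of week 2 and the final visit. Over 4 × 7 = 28 days, that leaves 28 − 3 = 25 days with no scheduled contact. Exposure is at most 50 participants × 28 days = 1,400 participant-days. That is a ceiling on exposure, not a risk estimate. The documents give no allergy rate, so no event count can be derived.

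**The case against.** The strongest reply is that both instructions can be obeyed. The 911 sentence makes no exception for symptoms that also appear in the mild list, and the mild sentence does not tell anyone to wait or to call the study team first. A participant who follows all of section 6.0 calls 911 and reports afterwards. This stands in part: it makes the fault a conflict between instructions and not a direction away from care. It does not help a participant who recognises the symptom in the mild list and stops there.

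A second reply is that the headings grade the symptoms, so mild tightening belongs in one list and severe tightness in the other. But the plan gives no threshold, and a lay participant has no means of grading the sensation.

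Third, participants act on consent forms and handouts, and the consent pages are not in the public copy. That is correct, and it limits the claim to the protocol text.

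Fourth, the risk is small. Known allergy is screened out, section 6.0 itself describes the risk of an unknown allergy as slight and severe reactions as not expected, and section 4.1 says that amounts in this range were "found to have only minor side effects, mainly stomach upset, bloating and nausea, and none of the side effects advanced to serious adverse events" in an earlier trial. A participant who calls the study team would also reach people with medical backing, although no response time is stated. All of this lowers the expected number of events. None of it removes the contradiction.

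Finally, because the severe paragraph is introduced by tree nuts, deleting the mild entry might seem to leave reactions to olive oil uncovered. The 911 sentence, however, is triggered by the symptom and not by the food.

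**Conclusion.** The concern holds. Section 6.0 attaches two instructions to throat tightness, and nothing in the document says which prevails. One symptom is affected and the other 11 entries are consistent. The probability of harm is low and the possible consequence serious, so the text should be corrected, but it does not threaten the study's results.

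The conclusion rests on reading tightening and tightness of the throat as the same symptom, which is how a participant would read them. It covers the protocol text only. Whether the duplication reached participants cannot be judged from what is public.

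**What to change.** Delete the throat-tightening entry from the mild list in section 6.0, so that throat tightness appears only in the tier that calls for 911. Make the same deletion in any consent form, handout or call script that repeats the lists.

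An optional clarification is to introduce the severe paragraph as applying to either study food.

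The cost is one phrase in the protocol and matching edits to participant materials. No visits, staff time or data collection are added, and no analysis changes.
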